Study Number: NCT02018562

Official Title: *Evaluation of a Tracheostomy Tube That Enables Communication*

Principal Investigator: [name]

Date: 12/19/2013

JHM IRB - eForm A – Protocol

Use the section headings to write the JHM IRB eForm A, inserting the appropriate material in each. If a section is not applicable, leave heading in and insert N/A.

- **When submitting JHM IRB eForm A (new or revised), enter the date submitted to the field at the top of JHM IRB eForm A.**

1. Abstract

- a. Provide no more than a one page research abstract briefly stating the problem, the research hypothesis, and the importance of the research.

Verbal communication greatly affects people’s autonomy and is directly related to how they perceive their quality of life (Hess, 2005). The need for effective communication is heightened during critical illness. Critically ill patients requiring mechanical ventilation often need an endotracheal tube or a tracheostomy tube. When a patient is intubated, communication is often accomplished through facial expressions, gestures, and/or writing, depending on the person’s neurological status and sedation level (Batty, 2009). However, these simple modes of communication are not always effective and can often result in frustration for the patient (Patak et al., 2006).

A benefit of tracheostomy over an endotracheal tube is that it may facilitate the ability to communicate by mouthing words. Additionally, when a person receives a tracheostomy tube, several methods used to elicit phonation can be utilized, including the use of a one-way speaking valve, leak speech, and digital occlusion. All of these methods require toleration of cuff deflation (Batty, 2009; Astrachan, Kirchner, & Goodwin, Jr., 1988; Hess, 2005; Nomori, 2004). Unfortunately, some critically ill mechanically ventilated patients cannot tolerate cuff deflation despite their ability to maintain arousal and to initiate meaningful communication. Uniquely designed tracheostomy tubes are available that enable speech and do not require cuff deflation. These “talking tracheostomy tubes” are rarely used because of a general lack of awareness among care providers. However, recently, at the Johns Hopkins Hospital, there has been an increase in the use of these tubes to facilitate speech. One of the tubes that has proven to be effective is the Blueline Ultra Suctionaid (BLUSA).

In 2010, we conducted a retrospective review of 4 cases and found that BLUSA tracheostomy helped facilitate communication in this unique population (IRB #: NA_00041547). Now, we would like to formally conduct a prospective study to evaluate the outcomes of patients using a BLUSA using a pretest-posttest research design.

Identifying the predictors of intelligibility and the impact of BLUSA on Quality of Life (QOL) and communication will promote communication between patients and healthcare providers. This empowers patients and allows healthcare staff to obtain a more accurate assessment of patients’ condition and tailor care accordingly.

2. Objectives (include all primary and secondary objectives)

Specific Aim 1: Determine the impact of a BLUSA on QOL in patients requiring prolonged mechanical ventilation in the hospital

Hypothesis 1a: The mean health-related QOL scores of patients who use BLUSA will be significantly higher compared to patients who do not use BLUSA.

Hypothesis 1b: The mean voice-related QOL scores of patients who use BLUSA will be significantly higher compared to patients who do not use BLUSA.

Specific Aim 2: Determine the outcomes of communication following the use of BLUSA in patients requiring prolonged mechanical ventilation in the hospital.

Hypothesis 2: Effectiveness of communication in patients who use BLUSA will be significantly improved compared to patients who do not use BLUSA.

Research Question 2a: What is the time to speech among patients who are unable to speak using a speaking valve?

Research Question 2b: What is the frequency and duration of speech with use of BLUSA?

Specific Aim 3: Identify the predictors of intelligibility in patients requiring prolonged mechanical ventilation in the hospital.

Hypothesis 3: Several factors such as age, sex, educational level, primary diagnosis, indications for mechanical ventilation, indication for tracheostomy, co-morbidities, and severity of illness will significantly contribute to speech intelligibility in patients requiring prolonged mechanical ventilation in the hospital.

Specific Aim 4: Validate the speech item in the health-related QOL instrument to evaluate speech as a domain of QOL in patients requiring prolonged mechanical ventilation in the hospital

Hypothesis 4: The mean health-related QOL scores will moderately correlate negatively with mean voice-related QOL (VR-QOL) questionnaire (criterion validity).

3. Background (briefly describe pre-clinical and clinical data, current experience with procedures, drug or device, and any other relevant information to justify the research)

1. Abstract from the prior study (IRB #: NA_00041547) that got accepted for publication in Journal of Medical Speech-Language Pathology:

Purpose: To describe the types of talking tracheostomy tubes available, present four case studies of critically ill patients who used a specialized tracheostomy tube to improve speech, discuss their advantages and disadvantages, propose patient selection criteria, and provide practical recommendations for medical care providers.

Method: Retrospective chart review of patients who underwent tracheostomy in 2010.

Results: Of the 220 patients who received a tracheostomy in 2010, 164 (74.55%) received a percutaneous tracheostomy and 56 (25.45%) received an open tracheostomy. Among the percutaneous tracheostomy patients, speech-language pathologists were consulted on 113 patients, 74 of whom were on a ventilator. Four of these 74 patients received a talking tracheostomy tube, and all four were able to speak successfully while on the mechanical ventilator even though they were unable to tolerate cuff deflation.

Conclusions: Talking tracheostomy tubes allow patients who are unable to tolerate cuff deflation to achieve phonation. Our experience with talking tracheostomy tubes suggests that clinicians should consider their use for patients who cannot tolerate cuff deflation.

2. Additionally, over the last couple of years, the use of BLUSA has increased dramatically at the Johns Hopkins Hospital.

4. Study Procedures

- a. Study design, including the sequence and timing of study procedures (Distinguish research procedures from those that are part of routine care).
Design: Prospective Pretest-Posttest design Clinical Trial – Pilot Study

Sequence and timing:

A. Pre – Assessment

1. Electronic Patient Records (POE, EPR, or EPIC)
 - a. Demographic Data
 - b. Patient Characteristics
 - c. Patient Outcomes
2. Patient Survey
 - a. Quality of life
 - b. Voice-Related quality of life

B. Intervention vs. Control Group

Intervention Group:

- a) The BLUSA trial involves placement of a BLUSA tracheostomy tube by respiratory therapist after obtaining an order from an authorized prescriber (MD, PA, or NP). The SLP sets up the tracheostomy tube for speech and then determines the optimal air flow required for voicing. This amount of air flow is communicated to the ICU staff for further use.
- b) We will ensure that the SLP meets with the patient for a minimum of 3 sessions within a week to optimize the use of a BLUSA.
 - i. SLP will also assess the duration of successful speech during each session
 - ii. Sentence intelligibility will also be assessed during the 3rd session. This session will be audio-taped and reviewed by a second rater for sentence intelligibility.
 - iii. SLP will determine the level of independence with BLUSA during the 3rd session.

Control Group:

- a) This group will also receive BLUSA trial as standard of care but a week later after the pre and post assessments have been completed

C. Post-Assessment

[figure not shown]
1. Electronic Patient Records (POE, EPR, or EPIC)
 - a. Patient Characteristics
 - i. Severity of Illness
 - b. Patient Outcomes
 - i. Time to BLUSA in days
 - ii. Time between speaking valve trial and BLUSA
2. Patient Survey
 - a. Quality of life
 - b. Voice-Related Quality of life
 - c. Level of independence to use of BLUSA
 - d. Patient satisfaction to use of BLUSA

Setting: All vented units at the Johns Hopkins Hospital (MICU, SICU, CICU, CCU, NCCU, WICU, Wbg 5D, Wbg 5C & MPCU)

Instruments:

Name	Concept measured	Number of items
QOL-MV	Quality of life in mechanically ventilated patients questionnaire	12
VR-QOL	Voice-related quality of life questionnaire	10
SIT	Sentence intelligibility test	11
SOFA	Sequential Organ Failure Assessment Tool	6
RASS	Richmond Agitation Sedation Scale	1
CAM-ICU	Confusion Assessment Method	4
Additional questions	Demographic Data Patient's independence and satisfaction with BLUSA	2

Study Protocol Flow Chart

Date: 12/19/2013

Principal Investigator: [name]

Application Number: NA_00086689

- b. Study duration and number of study visits required of research participants.
The study duration is estimated to be approximately 2 weeks per patient with a total of 5 visits by study team.
- c. Blinding, including justification for blinding or not blinding the trial, if applicable. Patients will not be blinded to intervention or control group.
- d. Justification of why participants will not receive routine care or will have current therapy stopped.
If patient is not willing to participate in the study, their routine care will not be altered. They will still have the opportunity to use BLUSA per current standard of care. Patients who are in the control group will also receive BLUSA but a week late.
- e. Justification for inclusion of a placebo or non-treatment group. N/A
- f. Definition of treatment failure or participant removal criteria.
If there is a change in clinical condition that prevents study team from continuing with the BLUSA trial or if the patient is discharged from the hospital, the patient will be dropped from the study.
- g. Description of what happens to participants receiving therapy when study ends or if a participant's participation in the study ends prematurely.
If participants receiving BLUSA complete the study (after the post-assessment), they will continue to use BLUSA per our current standard of care. If the participant's participation using BLUSA ends prematurely due to change in clinical condition, then they will be dropped from the study. But if their condition improves and warrants reuse of BLUSA, they will be offered BLUSA per our standards of care but will not be re-enrolled in the study.

5. Inclusion/Exclusion Criteria

Inclusion Criteria:

Mechanically ventilated via tracheostomy
Awake, alert, and attempting to communicate
Able to understand English

Exclusion Criteria:

Delirium
Fresh tracheostomy within 48 hours
Laryngectomy

6. Drugs/ Substances/ Devices

- a. The rationale for choosing the device to be used.
 - 1. Enables speech in patients who are mechanically ventilated and unable to tolerate cuff deflation.
 - 2. Over the last couple of years, the use of BLUSA has increased dramatically at the Johns Hopkins Hospital.
 - 3. Its impact on quality of life is unknown.
 - 4. This device has the speech attachment that the routine tracheostomy tubes do not have.
 - 5. This device' speech attachment has a wider lumen and is detachable for cleaning.
- b. Justification and safety information if FDA approved drugs will be administered for non-FDA approved indications or if doses or routes of administration or participant populations are changed. N/A
- c. Justification and safety information if non-FDA approved drugs without an IND will be administered. N/A

7. Study Statistics

- a) Primary outcome variables
 1. Quality of life
- b) Secondary outcome variables
 1. Sentence intelligibility
 2. Level of independence with BLUSA
 3. Patient satisfaction with BLUSA
- c) Variables of Interest
 1. Age, Sex, Race
 2. Indication for ICU admission
 3. Indication for Tracheostomy
 4. Severity of Illness (measured by SOFA scores)
 5. Delirium (CAM-ICU)
 6. Sedation (RASS)
 7. Motor Speech (Cranial nerve assessment V, VII, IX, X, and XII)
 8. Information about secretions (suction frequency, secretion quality and quantity)
 9. Time to SLP consult in days
 10. Time to initial in-line speaking valve trial
 11. Severity of Illness
 12. Time to BLUSA in days
 13. Time between speaking valve trial and BLUSA

d) Statistical plan including sample size justification and interim data analysis.

In order to compare changes in health-related quality of life from pre-assessment to post-assessment, we need 73 participants in each group. This allows for a 20% drop out rate and is based on a sample size of 61 individuals in each group to achieve 80% power and a clinically meaningful 20% increase in health-related QOL mean score from 61.16 (SD \pm 21.74) to 73.38 (SD \pm 26.09) based on another "Quality of Life in Mechanically Ventilated Patients" study by PI. We assume a two-tailed test with a significance level of $\alpha = 0.05$.

Interim data analysis will be conducted after 12 months of data collection. Mean, standard deviation, median and inter-quartile range will be calculated for continuous variables. Paired t-tests will be used to compare pre and post assessment scores for continuous variables. Frequencies and percentages will be calculated for categorical variables. Chi square and Fisher Exact tests will be used to compare pre and post assessment scores of categorical variables. Validation of the QOL instrument will include calculation of Cronbach's alpha, Pearson correlation, Kappa.

e) Early stopping rules.

Reasons for stopping data collection for a participant will include

1. change in clinical condition
2. discharge from the hospital

8. Risks

a. Medical risks, listing all procedures, their major and minor risks and expected frequency.

Administration of questionnaires repeatedly can be burdensome. In addition, questions about their quality of life while mechanically ventilated may be emotionally distressing.

b. Steps taken to minimize the risks.

If at any time the participant appears upset or distressed, the interviewer will stop the interview and refer to the medical team providing care in the ICU. The interviewer will remain with the participant until she or he has regained emotional equilibrium. If the participant states that he/she is tired and would like to rest, the interviewer will stop the interview and come back at a later time to continue with the interview. The participant may wish to withdraw from the study anytime they choose to.

Date: 12/19/2013

Principal Investigator: [name]

Application Number: NA_00086689

- c. Plan for reporting unanticipated problems or study deviations.
The PI will discuss any unanticipated problems of study deviations that pertain to the participants' health with the ICU team caring for the patient.
- d. Legal risks such as the risks that would be associated with breach of confidentiality.
Data will be stored in RedCap database that is password protected on the ICTR server. The database can only be accessed by the study team and the PI. Upon, completion of data collection, names and medical record numbers will be removed. A new research ID number will be assigned for analysis. Any document that may re-identify the patient will be destroyed. Once the data are de-identified, then analysis will begin.
- e. Financial risks to the participants. N/A

9. Benefits

- a. Description of the probable benefits for the participant and for society.
The participant may benefit personally from the proposed study because they will have the opportunity of spending additional time with SLP during the 3 sessions. Identifying the predictors of intelligibility and the impact of BLUSA on QOL and communication will promote communication between patients and healthcare providers. This empowers patients and allows healthcare staff to obtain a more accurate of patients' condition and tailor care accordingly.

10. Payment and Remuneration

- a. Detail compensation for participants including possible total compensation, proposed bonus, and any proposed reductions or penalties for not completing the protocol. N/A

11. Costs

- a. Detail costs of study procedure(s) or drug (s) or substance(s) to participants and identify who will pay for them. N/A

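### Hypothesis 2 claims better communication than in non-users, but no outcome is assigned to it, and the nearest candidate, sentence intelligibility, has no written baseline or non-user value

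*Combined protocol and SAP*

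**What the plan says.** Specific Aim 2 in section 2 is descriptive: "Determine the outcomes of communication following the use of BLUSA in patients requiring prolonged mechanical ventilation in the hospital". The hypothesis beneath it is comparative and claims significance: "Effectiveness of communication in patients who use BLUSA will be significantly improved compared to patients who do not use BLUSA".

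Section 7a gives quality of life as the primary outcome. Section 7b gives three secondary outcomes: sentence intelligibility, independence with BLUSA and satisfaction with BLUSA. None is linked to Hypothesis 2, and the instrument table in section 4a does not say which instrument measures effectiveness of communication.

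On timing, section 4a says under the Intervention Group: "Sentence intelligibility will also be assessed during the 3rd session". Of the control group it says: "This group will also receive BLUSA trial as standard of care but a week later after the pre and post assessments have been completed". The pre-assessment survey lists two questionnaires, quality of life and VR-QOL, and both appear again at post-assessment.

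For analysis, section 7d names paired t-tests for continuous variables, and chi-square and Fisher exact tests for categorical ones, in each case comparing pre with post.

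**The concern.** A claim of significant improvement over non-users needs three things: a defined outcome, a value of that outcome in non-users, and a test that sets the two groups against each other. For Hypothesis 2 the written plan supplies none of them. An analyst following it would have to choose the outcome later, and the most natural choice could not support the comparison.

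At stake is whether Hypothesis 2 can be answered at all. If it stays as worded, the final report must either leave it unanswered or answer it with something that the plan did not specify.

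**Working it through.** The point is structural, so most of the check sets the sections side by side.

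**1. The plan's only sample-size figure.** Section 7d powers health-related quality of life, not communication. Inputs: means 61.16 and 73.38, SDs 21.74 and 26.09, two-sided alpha 0.05, power 80%.
- Difference: 73.38 − 61.16 = 12.22.
- Averaged variance: (21.74² + 26.09²)/2 = 576.66, so SD = 24.01.
- n per group = 2 × (1.960 + 0.842)² × 576.66 / 12.22² = 60.6, rounded up to 61.

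This reproduces the stated 61 per group. It is a two-group calculation, although 7d then names only pre/post tests. For Hypothesis 2 the plan gives no instrument, SD or target difference, so no power can be computed. As a scale only, 61 per group gives 80% power for a difference of (1.960 + 0.842) × √(2/61) = 0.51 SD on a continuous measure, provided that it is taken in both groups.

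**2. Which outcome could serve.** Sentence intelligibility is the only strong candidate outside the quality-of-life questionnaires. The plan uses it elsewhere, as the outcome of the predictor question in Aim 3.

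**3. Where each candidate is written to be measured.**

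| Value needed | Intelligibility | VR-QOL |
|---|---|---|
| Intervention, pre | not listed | listed |
| Intervention, follow-up | third session | listed |
| Control, pre | not listed | listed |
| Control, follow-up before BLUSA | not listed | listed |

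Intelligibility has 1 of 4 values and VR-QOL has 4 of 4. The VR-QOL entries for controls follow because section 4a has controls complete both assessments before BLUSA and exempts them from no survey item.

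**4. Could a later control value help?** Controls receive BLUSA after their post-assessment. An intelligibility score taken then is a score with BLUSA in use and cannot stand for non-users.

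**5. Which tests remain.** A paired or pre/post test needs a pre value, and intelligibility has none in writing. A between-group test needs a control value without BLUSA, which is also absent, and 7d names no such test.

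**The case against.** The strongest reply is that the schedule may exist where it cannot be read. The flow chart is not shown, and the patient outcomes at pre-assessment are not itemised. This stands as a limit: the point covers the written procedures only. Even so, a measurement found in the flow chart would still need to be named in section 7 as the Hypothesis 2 endpoint.

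A second reply is that this is a secondary aim of a self-described pilot. That bears on its weight, but the plan still states a significance hypothesis.

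A third is that VR-QOL already covers communication. It is collected at the right times, but the plan gives it to Hypothesis 1b. It can carry the comparison only as that same test.

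A fourth is that intelligibility could simply be added to both assessments in both groups. That is legitimate, but it is new data collection, and the plan would have to say how to score a patient who produces no audible speech.

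A reader might also infer a wider failure, that none of the communication and device-use measures has a control value. The documents do not support counting them that way. Research Questions 2a ("What is the time to speech among patients who are unable to speak using a speaking valve") and 2b ("What is the frequency and duration of speech with use of BLUSA") are posed as descriptive questions. Independence and satisfaction concern use of the device, so they do not apply to controls who have not yet received it. Nor does it follow that speech data are collected only in the intervention group: controls also have a BLUSA trial later, and section 4b gives about two weeks and five visits without separating the groups.

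**Conclusion.** The point holds for Hypothesis 2 as written. No outcome is assigned to it. Intelligibility, the one strong candidate outside the quality-of-life questionnaires, has one of the four values needed, and the tests in 7d cannot make the stated comparison on it.

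This rests on the written text of sections 2, 4a and 7, and on the flow chart not adding a communication measure in both groups before controls receive BLUSA. If it does, what remains is only the failure to name the endpoint and a between-group test.

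A reader might infer that the sponsor means to report a users-only result as an improvement, or to count one VR-QOL difference as two findings. No section plans either, and neither is part of this conclusion. Nor does the point undermine quality of life as primary outcome, which is listed at both assessments. The change should be made, but the matter is confined to one secondary aim.

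**What to change.** 1. Restate Hypothesis 2 as descriptive among BLUSA users, in line with Aim 2. Report intelligibility and the speech measures as estimates with 95% confidence intervals and make no claim of improvement over non-users. Speech duration already has a collection step: "SLP will also assess the duration of successful speech during each session".
2. Rest any comparative communication claim on VR-QOL. Compare the groups at post-assessment with adjustment for the pre-assessment score, in place of the within-group paired test, and report this as the same single test as Hypothesis 1b. The written text does not say how patients are allocated to groups; baseline adjustment helps with chance imbalance but does not replace a stated allocation method.
3. If the flow chart already schedules a communication measure in both groups before controls receive BLUSA, name that measure in section 7 as the Hypothesis 2 endpoint instead, with a between-group test.

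The cost is mainly wording in sections 2 and 7; VR-QOL is already collected. The price is that Hypothesis 2 loses its separate significance claim, and the comparison that remains is patient-reported in a study where, by section 4c, patients know their group.

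### Hypothesis 4 predicts a negative correlation between two scales that Hypotheses 1a and 1b both read as higher = better, and it tests the whole QOL score instead of the speech item named in Aim 4

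*Combined protocol and SAP*

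**What the plan says.** Section 2 (Objectives) sets a direction for each scale under Aim 1. Hypothesis 1a expects BLUSA users to score higher on average than non-users on the health-related scale. Hypothesis 1b makes the same prediction for the voice scale: "The mean voice-related QOL scores of patients who use BLUSA will be significantly higher compared to patients who do not use BLUSA". Section 7d (sample size) treats a rise as benefit too, describing the change from 61.16 to 73.38 as "a clinically meaningful 20% increase in health-related QOL mean score".

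Aim 4 in the same section is to "Validate the speech item in the health-related QOL instrument to evaluate speech as a domain of QOL". Its only hypothesis is: "The mean health-related QOL scores will moderately correlate negatively with mean voice-related QOL (VR-QOL) questionnaire (criterion validity".

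The instruments table in section 4a lists QOL-MV ("Quality of life in mechanically ventilated patients questionnaire") with 12 items and VR-QOL with 10. It gives names, concepts and item counts, and no score range, direction, reverse coding or transformation. Nothing elsewhere in the document supplies these.

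The only analysis text for Aim 4 is one sentence in section 7d, which opens "Validation of the QOL instrument will include calculation of" and then names three statistics: alpha, a Pearson coefficient and Kappa. It does not mention the speech item or say which two variables the Pearson coefficient pairs.

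**The concern.** There are two separate problems.

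**Direction.** If a higher score means better on both scales, patients with better voice-related QOL should tend to have better health-related QOL, and criterion validity would show as a positive correlation. Hypothesis 4 would then treat agreement between the scales as evidence against validity. If instead a higher VR-QOL score means worse, Hypothesis 4 makes sense, but Hypothesis 1b then reads a worsening as benefit from the device.

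**Target.** The aim concerns one item; the hypothesis concerns the whole score. A whole-score correlation can come out moderate or near zero whether or not the speech item tracks voice-related QOL. The item could be reported as validated, or not, without having been tested.

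**Working it through.** **The plan's own figures.** There is no sample size, power or threshold for Hypothesis 4. The only computed figure is 61 per group for the primary comparison, which fixes the number of completers used below. It reproduces:

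- difference = 73.38 − 61.16 = 12.22
- SD = √((21.74² + 26.09²)/2) = 24.01
- n = 2 × (24.01 × (1.960 + 0.842)/12.22)² = 60.6, rounded up to 61 per group, or 2 × 61 = 122 in total

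Planned enrolment is 2 × 73 = 146.

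**Direction: the readings side by side.** QOL-MV is taken as higher = better, on the strength of Hypothesis 1a and section 7d.

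| Scoring of VR-QOL | Hypothesis 1b (higher with BLUSA) | Hypothesis 4 (negative correlation) |
|---|---|---|
| Higher = better | Benefit: coherent | Wrong sign for criterion validity |
| Higher = worse | Predicts harm: wrong direction | Coherent |
| Scored differently in the two hypotheses | Possible | Possible, but not stated anywhere |

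This is an inconsistency of scale direction, not a mathematical contradiction: Hypotheses 1a and 1b concern group means, Hypothesis 4 concerns association between patients, and both means can rise while scores correlate negatively within groups.

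**Target: how much one item in twelve moves the total.** The documents give no item-level data. Assumptions: 12 items of equal variance and a common inter-item correlation r, shown at 0.1 / 0.3 / 0.5. Let s be the speech item's correlation with VR-QOL and c that of each of the other 11 items. Values are absolute, so they apply to either sign.

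- SD of the sum of 12 unit-variance items = √(12 + 132r) = 5.02 / 7.18 / 8.83
- correlation of total with VR-QOL = (s + 11c)/SD

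| | r = 0.1 | r = 0.3 | r = 0.5 |
|---|---|---|---|
| Change in total correlation when s goes from 0 to 0.5, c fixed (0.5/SD) | 0.10 | 0.07 | 0.06 |
| c at which total = 0.30 with s = 0 (0.30 × SD/11) | 0.14 | 0.20 | 0.24 |
| c at which total = 0.50 with s = 0 (0.50 × SD/11) | 0.23 | 0.33 | 0.40 |

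Both 0.30 and 0.50 are shown because the protocol puts no number on a moderate correlation. The correlation matrices implied by the s = 0 cases are all positive definite (smallest eigenvalue 0.218), so the cases are mathematically possible.

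**Precision for comparison.** Fisher z interval for a correlation of 0.30: atanh(0.30) ± 1.96/√(n − 3), transformed back.

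- n = 122: 0.13 to 0.45
- n = 146: 0.14 to 0.44

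At either size the interval extends about 0.15 on each side, more than the largest shift in the first row of the table (0.10).

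**The case against.** Several points can fairly be made for the plan.

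- **The direction is inferred.** No scoring rule is quoted, and for VR-QOL the reading of higher as better rests on Hypothesis 1b alone. This stands, and it is why one cannot say which hypothesis is wrong. It does not remove the conflict, because no single scoring of VR-QOL makes Hypotheses 1b and 4 both sensible.
- **There is no pass/fail rule.** A Pearson coefficient is reported with its sign, so an analyst would notice a positive value. This softens the consequence: a wrong conclusion is not automatic. The prespecified hypothesis would still be mis-signed.
- **The analysis list in section 7d is not exhaustive.** An item-level correlation is not excluded, and the item responses will exist. True, but Hypothesis 4 is the only stated test of Aim 4 and it names the mean score. The 12-item length also comes from the instruments table, assuming QOL-MV is the health-related QOL measure; it is the only general QOL questionnaire listed.
- **The numerical scenario is extreme.** A speech item with zero correlation to VR-QOL, while sharing r with 11 items that do correlate, implies a negative partial correlation given the sum of those 11: −0.08 / −0.20 / −0.32 for a total of 0.30, and −0.15 / −0.37 / −0.60 for a total of 0.50. At r = 0.5 this is implausible. The conclusion does not need it; the 0.06 to 0.10 shift already shows how little weight the item carries, though that figure also holds the other items fixed.
- **This is the last aim of a pilot,** and validation is not among the listed primary or secondary outcomes. That limits the reach of the problem. It does not make the hypothesis right.

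**Conclusion.** The concern holds on both counts. As written, the sign in Hypothesis 4 conflicts with Hypothesis 1b under any single scoring of VR-QOL, and the documents do not show which should change. Hypothesis 4 also does not test Aim 4: under the stated item assumptions, a 0.5 change in the speech item's own correlation moves the total-score correlation by 0.06 to 0.10, less than the sampling uncertainty at the planned size. The textual findings rest on no assumption beyond reading QOL-MV as the health-related QOL instrument; the size rests on equal item variances, a common inter-item correlation of 0.1 to 0.5 and fixed correlations for the other items. The effect is confined to Aim 4 and the reading of Hypothesis 1b. It should be corrected, but the primary QOL comparison and the 61 per group are untouched.

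**What to change.** 1. State once, beside the instruments table, the scoring direction of QOL-MV and VR-QOL and any transformation, and use that scoring throughout.
2. Reconcile the hypotheses with it. If higher is better on both scales, make Hypothesis 4 a positive correlation. If higher VR-QOL is worse, reverse Hypothesis 1b.
3. In section 7d, make the Aim 4 test the correlation, with 95% CI, between the QOL-MV speech item and the VR-QOL total score. Keep the total-score correlation as supportive. The planned Pearson coefficient can stay; a rank correlation and a corrected item-total correlation are optional.
4. While editing that line, it would help to give the numeric range meant by moderate and to say which assessment supplies the data, with one record per participant. These are clarifications and not part of the defect.

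The cost is one scoring statement, a rewording of Hypothesis 4 or 1b, and one analysis line. Both questionnaires are already given at the pre- and post-assessments (section 4a), so no participants, visits or data items are added.
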